### **9.3.1.2 Enrolled Subjects**

Subjects who received at least one dose of placebo drug during the Run-in Period are considered enrolled.

### **9.3.2 Study Day**

In this study, subjects will receive placebo in a 6-week single-blind placebo Run-in Period. Day 1 will be the first dose date of placebo in the Run-in Period. Study Day, which follows the Clinical Data Interchange Standards Consortium (CDISC) Study Data Tabulation Model (SDTM) standard, is defined as (Assessment date - date of first study drug dosing + 1 day), where the assessment date is on or after the date of first study drug dosing; (Assessment date - date of first study drug dosing), where the assessment date is before the date of first study drug dosing.

### **9.3.3 Treatment Study Day**

Randomized treatment will not begin until Week 6, Treatment Study Day 1 is therefore defined as the first dose date in Period A following the same format as Study Day. Visits will be summarized using Study Day, and treatment day will be included in select listings.

### **9.3.4 End of Study Treatment Definition**

A subject is considered to have completed the main study treatment period if they completed the Week 76 visit. The end of study treatment is defined as the date of the last dose of study drug.

### **9.3.5 End of Study Definition**

A subject is considered to have completed the main study if the subject has completed the three parts of the Treatment Period, including the final follow-up visit

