PRN telephone contacts regarding GC adjustment ²³												X	X						
Review study diary/drug adherence ²⁴	X	X	X	X	X	X	X	X	X	X	X	X	X	X	X	X	X	X	
Review AEs	X	X	X	X	X	X	X	X	X	X	X	X	X	X	X	X	X	X	
Physical examination ²⁵	X		X	X		X	X	X		X	X	X	X		X	X	X	X	
Acne IGA score ²⁶				X			X									X		X	
Hirsutism mFG score for females ²⁶				X			X									X		X	

Abbreviations: 17-OHP, 17-hydroxyprogesterone; A4, androstenedione; ACTH, adrenocorticotrophic hormone; AE, adverse event; ALP, alkaline phosphatase; ALT, alanine aminotransferase; AST, aspartate aminotransferase; CGI-I, Clinical Global Impression – Improvement Scale; C-SSRS, Columbia–Suicide Severity Rating Scale; EC, Ethics Committee; ECG, electrocardiogram; EDC, electronic data capture; ET, early termination; FCP, female of childbearing potential; FSH, follicle-stimulating hormone; GC, glucocorticoid; GGT, gamma-glutamyl transferase; HADS, Hospital Anxiety and Depression Scale; HbA1c, hemoglobin A1c; HC(e), hydrocortisone (equivalents); HIV, human immunodeficiency virus; HOMA-IR, homeostatic model assessment of insulin resistance; IGA, Investigator's Global Assessment (score for acne); INR, international normalized ratio; IRB, Institutional Review Board; LH, luteinizing hormone; mFG, modified Ferriman-Gallwey (score for hirsutism); PGIC, Patient Global Impression of Change; PK, pharmacokinetics; PRN, as needed; PROs, patient-reported outcome measures; PT, prothrombin time; PTT, partial thromboplastin time; RTSM, randomization and trial supply management (system); SF-36, Short Form 36; SHBG, sex hormone-binding globulin; T, telephone contact; TART, testicular adrenal rest tumor; V, study visit.

Footnotes from 1.3.3 Schedule of Post-Screening Activities:

¹ Subjects who do not continue to the optional Open-Label Extension Period upon completion of Treatment Period Part C will enter a 30-day Follow-up Period.

² For subjects who continue to the optional Open-Label Extension Period, Week 76 will be considered Study Visit Number 1 for optional Open-Label Extension Period.

³ All study visits and telephone contacts should be performed on the indicated study days. In cases where adherence to the foregoing schedule is not possible, all activities for study visits and telephone contacts after the Week 0 visit must be completed within a ± 3-day window after the indicated study days.

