- **Part C:** During the last 46 weeks of the Treatment Period, all subjects will be escalated to 200 mg QD, with periodic opportunities for GC adjustment for eligible subjects. Subjects and Investigators will continue to remain blinded to previous treatment in Part A and dose level of tildacerfont in Parts B and C.
 - Subjects with A4 ≤ULN at Week 38 or Week 46 will begin to reduce their daily GC dose level by increments of approximately 5 mg/day HCe each time, down to a minimum of 15 mg/day HCe (see [Section 6.5.1.4](#)).
- For subject's continuing into the optional Open-Label Extension Period
 - The Open-Label Extension Period will provide subjects with up to 240 weeks of treatment with tildacerfont 200 mg QD.
 - Subjects will be eligible to adjust GC dose level at each visit (see [Section 6.5.1.4](#)).
- A 30-day *Follow-up Period at EOT*
 - Subjects who do not continue to the Open-Label Extension Period upon completion of Treatment Period Part C will enter a 30-day Follow-up Period.
 - Upon completion of the Open-Label Extension Period, subjects will enter a 30-day Follow-up Period.
 - At the end of study treatment, subjects will maintain the GC regimen and mineralocorticoid regimen (as applicable) established during Part C until the 30-day follow-up visit unless the Investigator determines that the subject's clinical status necessitates a dosing change. After completion of the study, GC therapy will be managed at the discretion of the subject's treating physician.

Changes in GC dosing are generally not permitted during this study except after certain visits in Part C, the optional Open-Label Extension Period, and in the case of stress dosing throughout the study. During times of clinically significant physical stress such as intercurrent illness with fever, surgical procedures, or

significant trauma, stress dosing with extra GC (in the form of HC) for prevention of adrenal crisis will be allowed according to “sick day guidelines” (see [Section 6.5.1.5](#)).

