4.1.2 Study Visits and Telephone Contacts

4.1.2.1 Study Visit Schedule

- During the Screening Period:
 - Screening Visit at ≤45 days before Day 1
 - Optional A4 Screening Visit ≤45 days before Day 1
- During the Run-in Period: visits at Day 1 and Week 4; scheduled telephone contact at Week 2
- During the Treatment Period:
 - Part A: visits every 4 weeks, at Week 6 (baseline) and at Weeks 10, 14, and 18; scheduled telephone contact at Week 8
 - Part B: visits every 6 weeks, at Weeks 24 and 30; scheduled telephone contact at Week 21
 - Part C: visits every 6 to 12 weeks, at Weeks 38, 46, and 58, 70, and 76; scheduled telephone contact at Week 52
- During the optional Open-Label Extension Period: Visits every 3 to 6 months at Weeks 88, 100, 124, 148, 172, 196, 220, 244, 268, 292 and 316
- At 30 days after the last dose of study drug for final safety follow-up
- PRN telephone contacts are detailed in [Section 4.1.2.3](#).

4.1.2.2 Mode of Study Visits in the Context of COVID-19 or Other Logistical Challenges

All efforts should be made to conduct visits in the clinic. Since the COVID-19 pandemic is expected to continue during the conduct of this trial, study visits can be adapted into a combination of in-clinic and telemedicine activities, with optional at-home visits, to mitigate the risk of COVID-19 infection associated with study participation and to accommodate local and individual circumstances while maintaining participant access to healthcare resources.

Some of the clinic activities of the Screening Visit may be conducted remotely (at the subject’s home) if approved by the site’s IRB/EC.

The EDC system will capture the mode by which data are collected for each visit/activity.

If home visits are conducted, the qualified medical professionals who will perform the study’s home visits are defined as individuals who meet national/local licensing requirements needed to perform the procedures required at the home visits. Their national/local licensure will be verified, and they will complete training on the study protocol and GCP. If the medical professional does not meet the national/local licensing requirements needed to perform the optional home visit activities (physical examination, acne IGA score, and hirsutism mFG score for females), the Investigator or Investigator-delegated study personnel must complete these activities for each visit.

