## 5 STUDY DESIGN

This is a multi-center, randomized, double-blind, placebo-controlled, dose-ranging clinical study with a 3-part Treatment Period and an optional Open-Label Extension Period. The 3-part Treatment Period will evaluate the efficacy and safety of up to 70 weeks of treatment with tildacerfont in adult subjects with classic CAH who have elevated biomarkers at baseline. At least 72 adult subjects will be randomized into the Treatment Period of the study.

A 6-week, single-blind, placebo Run-in Period, will assess subjects for adherence to their existing GC therapy and daily ingestion of placebo with food. Upon completion of a 6-week single-blind, placebo Run-in Period, subjects who meet all eligibility criteria will be randomized into the Treatment Period. Subjects will be randomized in a 1:1:1:1 ratio to receive either tildacerfont at a dose of 50 mg (once daily) QD, 100 mg QD, and 200 mg QD or matching placebo along the randomization stratum (Week 4 A4  $\leq$  4  $\times$  upper limit of normal [ULN] versus Week 4 A4  $>$  4  $\times$  ULN). The first 12 weeks of the treatment period constitute the randomized, double blind, placebo-controlled, dose finding treatment period (Part A).

Following Part A, all subjects will receive tildacerfont for duration of 12 weeks (Part B) with opportunities to up-titrate their tildacerfont dose up to 200 mg QD based on treatment response. Placebo subjects will receive the 100 mg tildacerfont QD dose at the beginning of Part B. Part B will have possible dose escalations at Week 18 and Week 24 for eligible subjects not meeting androstenedione (A4) response criteria as an assessment of dose titration for non-responders (A4  $>$  upper limit of normal [ULN]).

Part C is a 46-week treatment period in which all subjects are escalated to receive 200 mg tildacerfont QD at Week 30, with opportunities for glucocorticoid (GC) reduction for eligible subjects (subjects meeting A4  $\leq$  ULN).

Subjects continuing into the optional Open-Label Extension Period will receive 200 mg tildacerfont QD for up to 240 weeks of treatment, with opportunities for GC adjustment for eligible subjects at each visit. Upon completion of the Open-Label Extension Period or completion of Treatment Period Part C for those subjects who do not continue into the Open-Label Extension Period, subjects will return to the clinic within 30 days following their last dose for a Follow-up visit.

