## 15 CHANGES RELATIVE TO THE PROTOCOL-SPECIFIED ANALYSIS

Protocol Section 4.4.1 defines the completion of study treatment as completing “all visits through Week 76 of the Treatment Period.” In the SAP [Section 9.3.4](#), the end of study treatment is redefined to the completion of the Week 76 visit to remove the ambiguity surrounding the classification of subjects with missed or out-of-window visits.

Protocol Section 4.4.2 defines the end of the study as completing “all phases of the study, including the final follow-up visit.” In the SAP [Section 9.3.5](#), the end of study treatment is clarified as the completion of the three Treatment Period parts as well as the final Follow-up visit

Protocol Section 8.1.2.2 identifies the Patient Global Impression of Change and Protocol Section 8.1.2.2 identifies the Clinical Global Impression – Improvement Scale as efficacy assessments that evaluate the quality of life. Given that the protocol synopsis and Protocol Section 3 Objectives and Endpoints do not mention PGIC and CGI-I as efficacy assessments, these assessments will be listed as described in SAP [Section 14.6](#).

The mITT Population was defined in Protocol Section 9.3 as all randomized subjects who receive at least 1 dose of study drug (tildacerfont or placebo), have at least 1 A4 assessment, and did not change background GC through Week 18. This definition has been updated to specify

that subjects must have at least one post-baseline A4 assessment in order to make this population relevant to the efficacy analyses.

The Per-Protocol Analysis Set for each part of the Treatment Period was defined in Protocol Section 9.3 as all eligible subjects who have no major protocol deviations that would affect the analysis of efficacy data. This definition has been updated to only pertain to Part A of the Treatment Period in order to align with the analyses of the primary and secondary endpoints.

Since Protocol Section 6.1 defines study drug as either tildacerfont or placebo, the Safety Analysis Set should include all subjects treated with study drug, which includes the single-blinded placebo Run-in Period. The SAP [Section 8.4](#) therefore defines the Safety Analysis Set as subjects who receive at least one dose of study drug during the Run-in or Treatment Period, and the SAP [Section 8.5](#) defines the Randomized Safety Analysis Set to serve the intention of the protocol-defined Safety population defined in Protocol Section 9.3.

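### SAP 9.3.5 makes main-study completion depend on a follow-up visit that subjects still in the extension will not have had at the main data cut

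*SAP*

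**What the plan says.** SAP 9.3.5 defines a main-study completer as a subject who "has completed the three parts of the Treatment Period, including the final follow-up visit". SAP Section 15 lists this among the changes from the protocol and describes it as "clarified as the completion of the three Treatment Period parts as well as the final Follow-up visit". Neither place makes an exception for subjects who enter the extension.

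The protocol gives the follow-up visit after Part C to one group only. Footnote 1 of Section 1.3.3 reads: "Subjects who do not continue to the optional Open-Label Extension Period upon completion of Treatment Period Part C will enter a 30-day Follow-up Period". For the others, footnote 2 says that "Week 76 will be considered Study Visit Number 1 for optional Open-Label Extension Period", and Section 4.1.1 places their follow-up later: "Upon completion of the Open-Label Extension Period, subjects will enter a 30-day Follow-up Period". SAP Section 5 has the same split, with a follow-up visit either after the extension or upon "completion of Treatment Period Part C for those subjects who do not continue into the Open-Label Extension Period, subjects will return to the clinic".

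SAP 9.3.4 defines a separate milestone, completion of the main treatment period, for which the Week 76 visit alone is enough. SAP 11.1.2 says that the disposition summary covers Parts A, B and C, but not which definition of completion it tabulates.

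**The concern.** The definition and the visit schedule do not fit together. A subject who attends Week 76 and rolls over has done everything the main study asks, yet lacks the visit that 9.3.5 requires. The visit is not missed; the schedule places it after the extension.

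The source of the mismatch can be traced. Protocol 4.4.1 requires the final follow-up visit for completion of the whole study, all phases included. That works, because every subject's last phase ends in follow-up. The SAP narrowed the concept to the main study but kept the follow-up condition. SAP Section 4 says that the SAP governs where the two documents differ, so the narrowed rule is the one that would be programmed.

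At stake is the main-study completion rate in the report that covers results to Week 76/80. Read literally, the rule would deny completion to subjects who, under protocol 4.4.2, had to complete all Treatment Period visits successfully before they could enter the extension.

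**Working it through.** **Inputs**
- Screening of at most 45 days, run-in of 6 weeks, treatment of 70 weeks, follow-up of 30 days (SAP Section 5).
- Extension length: "The Open-Label Extension Period will provide subjects with up to 240 weeks of treatment with tildacerfont 200 mg QD" (protocol 4.1.1).
- Follow-up timing: "At 30 days after the last dose of study drug for final safety follow-up" (protocol 4.1.2.1).
- Final analysis after the last subject's Week 76 visit (SAP 10.3); main report to Week 76/80 (protocol 9.5).
- 72 subjects and 15% assumed dropout during the Treatment Period (SAP Section 7).
- Extension uptake q: not given in the documents, so assumed.

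**The plan's own durations reproduce**
- Main study: 45/7 + 6 + 70 + 30/7 = 86.7, rounded up to 87 weeks, as in SAP Section 5.
- With the extension: 86.7 + 240 = 326.7, rounded up to 327 weeks, as in SAP Section 5.

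**When the follow-up visit falls**
- Subjects who do not enter: 76 + 30/7 = 80.3, the Week 80 visit.
- Entrants who finish the extension: 76 + 240 + 30/7 = 320.3, the Week 320 visit.
- Gap from Week 76 for those entrants: 240 + 30/7 = 244.3 weeks, about 4.7 years.

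**The two SAP definitions at the main data cut**

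| Subject with Week 76 done | 9.3.4, main treatment period | 9.3.5, main study |
|---|---|---|
| Not in extension, Week 80 visit done | completed | completed |
| In extension, still on drug | completed | not completed |
| Entered extension, stopped early, follow-up done before the cut | completed | completed |

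Under 9.3.5, of two entrants, the one who has stopped can count as a main-study completer while the one who continues cannot.

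**Possible size, if disposition uses 9.3.5**

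Subjects reaching Week 76: 0.85 × 72 = 61.2, taken as 61, and 61/72 = 85%. Suppose that a share q of the 61 enters and is still in the extension at the cut, and that all the rest attend the 30-day follow-up. The rate under 9.3.5 is then 61 × (1 − q)/72:
- q = 0%: 61/72 = 85%
- q = 25%: 45.75/72 = 64%
- q = 50%: 30.5/72 = 42%
- q = 90%: 6.1/72 = 8%

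The shortfall is 61q/72, which is 42 percentage points at q = 50% and 76 at q = 90%.

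**The case against.** The strongest reply is that 9.3.4, immediately before, already handles entrants correctly, and that a disposition table organised by Parts A, B and C fits 9.3.4 at least as well as 9.3.5. The table shells are in a separate document. The Week 76/80 scope of the main report can also be read as Week 76 for entrants and Week 80 for everyone else. On this view 9.3.5 only needs clarifying.

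Much of that stands, and it limits what can be claimed. A reader might infer several stronger things that the documents do not support:
- **That every entrant will be reported as a non-completer.** SAP 11.1.2 does not cite 9.3.5, so misreporting follows only if 9.3.5 is the definition tabulated.
- **That no entrant can have the visit before Week 320.** Week 320 is the latest scheduled point. Follow-up is tied to the last dose, and the extension lasts up to 240 weeks and may be closed early (protocol 4.4.2).
- **That discontinuation rates are inflated.** Protocol 7.1 and 7.2 have discontinuation and withdrawal recorded by date and reason. Failing 9.3.5 creates no such record.
- **That the rule penalises the best responders, or one arm more than another.** Entry to the extension depends on completing visits, not on response. The documents give no roll-over by arm, and all subjects are assigned 200 mg QD from Week 30.
- **That efficacy is touched.** The ITT set is defined regardless of completion, no other analysis set uses 9.3.5, and the primary and secondary analyses are at Week 18.

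The reply does not remove the defect. The SAP holds two completion definitions that disagree for every entrant still in the extension at the cut, and no rule for choosing between them. Protocol 9.5 does place its final analysis after the last follow-up visit, but that does not help: SAP 10.3 triggers the final analysis at Week 76, and the main report stops at Week 76/80.

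**Conclusion.** The concern holds as a fault in a definition. SAP 9.3.5, repeated in Section 15, requires a visit that the schedule does not give to extension entrants until after the extension. Any entrant still in the extension at the main data cut fails the rule despite finishing Week 76, which is at odds with 9.3.4. This conclusion needs no assumption about uptake.

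The effect on a reported figure is conditional. If disposition uses 9.3.5, the completion rate is understated by the share of subjects who roll over. The illustrative fall from 85% to between 42% and 8% rests on four assumptions: the planned 15% dropout, an assumed uptake of 50% to 90%, no entrant having follow-up before the cut, and every non-entrant attending follow-up. The consequence is confined to descriptive disposition. It is worth correcting because the figure would otherwise conflict with the trial's own visit schedule.

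**What to change.** In SAP 9.3.5, define main study completed as: Week 76 visit done AND (entered the extension OR completed the 30-day follow-up visit). Align the Section 15 text, which at present also describes the 9.3.5 change as concerning the end of study treatment, and state in 11.1.2 that the disposition summary uses this definition.

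Under the illustration above, the rate becomes (61q + 61(1 − q))/72 = 61/72 = 85% whatever the uptake.

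The cost is one sentence in 9.3.5 and matching edits in two other places. No new data are needed, since SAP Table 7 already takes the first extension dose from the Week 76 dispensation. No visit, treatment rule or efficacy analysis changes.

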### **9.3.6 Age**

Age (years) is captured by the Demographics eCRF form at the Screening Visit.

### **9.3.7 Age at Diagnosis of CAH**

Age (in years) at diagnosis of CAH is captured in the Congenital Adrenal Hyperplasia History eCRF form at the Screening Visit.

### 9.3.8 Body Mass Index

Body mass index (BMI, kg/m^2) is derived as weight (kg) / [height (m) × height (m)]. Height measured at Screening will be used to calculate BSA. Body mass index may be summarized using the classifications defined in [Table 2](#).

**Table 2 Classification of Body Mass Index**

Parameter	BMI (kg/m  )
Underweight	< 18.8
Normal Range	18.5 -< 25
Overweight	25 -< 30
Obese Class I	30 -< 35
Obese Class II	35 - < 40
Obese Class III	≥ 40

### 9.3.9 Body Surface area

Body surface area (BSA) is calculated per the Mosteller formula as  $\text{sqrt}((\text{height (cm)} \times \text{weight (kg)})/3600)$ . Height measured at Screening will be used in all BSA calculations.

### 9.3.10 Baseline Values

Baseline values of serum biomarkers (i.e., A4, 17-OHP, and ACTH) are defined as the average of the Day 1, Week 4 and Week 6 assessments that are on or prior to the date of the first dose of double-blind study drug during Part A, allowing for unscheduled assessments to be windowed and replace missed scheduled visits. Visit windowing conventions will be used to identify the assessments that are used to construct baselines (see [Section 9.4](#)). Day 1 values are defined as the last non-missing assessment up to Day 14 for hormone assessments. For all other parameters, baseline values are defined as the last non-missing assessment prior to the first dose of randomized, double-blind study drug in Part A of the study. The following [Table 3](#) provides a guide for the baselines to use in analysis.

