#### **9.3.12 Percent Change from Baseline**

Percent change from baseline is calculated for the individual subject as the change from baseline divided by the baseline assessment and multiplied by 100%.

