#### **9.3.13 Change from Baseline on the Log Scale**

The change from baseline on the log scale is calculated as the difference of the log (post-baseline assessment) subtracted by the log (baseline assessment). It is also mathematically equivalent to the log of the ratio of the post-baseline assessment divided by the baseline assessment.

$$\begin{aligned} \text{change from baseline on the log scale} &= \log(\text{post baseline assessment}) - \log(\text{baseline assessment}) \\ &= \log \left( \frac{\text{post baseline assessment}}{\text{baseline assessment}} \right) \end{aligned}$$

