### 9.3.14 Geometric Mean Ratio and Percent Change

For efficacy variables of A4, 17-OHP, and ACTH, the geometric mean ratio (GMR) and percent change from baseline will be calculated by treatment group and dose level. The GMR is derived from the natural logarithm of the post-baseline value divided by the baseline value [ $\log(\text{post-baseline}/\text{baseline})$ ]. The GMR is the exponential function of the mean of  $\log(\text{post baseline}/\text{baseline})$ . The 95% CI of GMR is the exponential function of the 95% CI of the mean [ $\log(\text{post baseline}/\text{baseline})$ ]. The percent change is derived as  $100 \times (\text{GMR} - 1)$ . The 95% CI of percent change is  $100 \times (95\% \text{ CI of GMR} - 1)$ .

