### 13.3.3 Dose Response Modeling and Testing

Statistical testing for dose response will be performed using the repeated measures random coefficients mixed-effects model described in [Section 13.3.2](#). A4 values will be log transformed prior to analysis. The model will comprise of the log A4 change from baseline through to study Week 18, i.e. though 12 weeks of double blind randomized treatment; note the actual time, in days, from baseline to each post baseline A4 value through to study week 18 will be used in this analysis. Randomized treatment group and sex will be included in the model as class factors and baseline GC dose (in HCe) as continuous covariate. Subject specific intercept, time (in days)

and time x time random effects will be included. Further, randomized treatment by time and randomized treatment by time x time interactions will be included. The model will be fitted using maximum likelihood estimation. If the variance component for time or time x time are estimated to be zero then the corresponding term (or terms) will be retained in the model as fixed effects and the analysis re-run.

To test the union intersection hypothesis  $H_{0L} \cap H_{QL}$ , the model will be fitted with and without the randomized treatment by time and randomized treatment by time squared interactions terms. The difference in -2 log likelihood between models will be compared to the  $\chi^2_{df}$  cumulative distribution function on the appropriate degrees of freedom (i.e.  $df = 6$ ), this will provide the p-value to determine if the union intersection hypothesis can be rejected at the 10% alpha level; if so then there is evidence for a treatment effect of tildercerfont over placebo.

The fitted A4 change from baseline versus time profile will be extracted from the model for each randomized treatment and displayed graphically, superimposed upon the A4 time profiles for individual subjects.

Note, the programming of the repeated measures random coefficients mixed-effects model is particularly complex, hence example SAS codes perform the analysis are presented in Appendix D.

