#### **13.3.4 Summary of Descriptive Statistics for A4**

Descriptive statistics (11-point) for the serum A4 assessments, change from baseline in serum A4, and % change from baseline in serum A4 will be presented by scheduled time point (i.e., Baseline [serum A4 only], study Week 10, Week 14, and Week 18). Geometric means and geometric mean change from baseline, along with the associated log scale SDs will also be presented.

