### 13.4.1 First Secondary Efficacy Analysis

The First Secondary Efficacy Analysis (see [Table 1](#), Analysis 2.1) relates to the change from baseline in A4 as assessed on the log scale after 12 weeks on double-blind, placebo-controlled treatment. This analysis will be achieved as an integral part of the dose response modelling as described in [Section 13.3.3](#).

The estimated mean change from baseline in log A4 values at 4, 8 and 12 weeks of double blind randomized treatment will be extracted from the model by treatment arm as will the difference and associated 95% CI and p-value between each tildacerfont dose and placebo at each of 4, 8 and 12 weeks. To facilitate ease of interpretation, the estimated mean change from baseline in log A4 for each tildacerfont dose and placebo will be back transformed resulting in the estimated ratio of geometric means to baseline, i.e. the back transformed log scale estimated mean change becomes  $\{\text{estimated A4 geometric mean at time } x\}/\{\text{estimated A4 geometric mean at baseline}\}$  = GMR. Hence, GMR – 1 becomes the percentage CFB in geometric means. Further, the difference between each tildacerfont dose and placebo in estimated mean change from baseline in log A4 (along with the associated 95% CI) will also back transformed resulting in the ratio of  $\{\text{A4 GMR tilda at time } x\}/\{\text{A4 GMR placebo at time } x\}$  as the measure of treatment effect. And, again,  $\{\text{A4 GMR tilda at time } x\}/\{\text{A4 GMR placebo at time } x\} - 1$  becomes the percentage reduction (or increase) in geometric mean A4 values at time  $x$  for tildacerfont compared to placebo.

In addition orthogonal linear and quadratic contrasts between treatments at 12 weeks of double blind randomized treatment will also be estimated as a supportive measure of dose response at this time point.

Example SAS codes in relation to the First Secondary Efficacy Analysis are provided in Appendix D.

A serial plot will be presented of the estimated mean change from baseline in log A4 over time. The y-axis will be the percent CFB (i.e  $100 \{ \exp(\text{estimated change from baseline in log A4}) - 1 \}$ ) and the x-axis will represent the Part A visits, baseline, Week 4, Week 8, and Week 12 of double blind randomized treatment. All treatment groups will be presented on the graph.

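### Averaging the three hormone baselines on the raw scale builds a downward offset into every within-arm log-scale percent change, placebo included; drug-placebo contrasts are unaffected

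*SAP*

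**What the plan says.** SAP 9.3.10: baseline values of A4, 17-OHP and ACTH "are defined as the average of the Day 1, Week 4 and Week 6 assessments" taken on or before the first double-blind dose. Unscheduled samples may stand in for missed visits. The section does not say on which scale the average is taken.

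SAP 9.3.13 defines log-scale change as log(post-baseline) minus log(baseline). SAP 9.3.14 continues: "The GMR is the exponential function of the mean of" log(post-baseline/baseline), with percent change equal to 100 × (GMR - 1), given by treatment group and dose level.

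SAP 13.4.1 takes the same quantity from the model for each arm at 4, 8 and 12 weeks. There, GMR - 1 "becomes the percentage CFB in geometric means", and a plot shows percent change by arm from baseline onward. The treatment effect is the ratio of the drug GMR to the placebo GMR; that ratio minus 1 "becomes the percentage reduction (or increase) in geometric mean A4 values".

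SAP 13.4.2 and Appendix E convert the log-scale results into absolute changes. SAP 13.4.4, 13.4.5 and 13.5.8 repeat the approach for 17-OHP and ACTH.

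**The concern.** SAP 13.4.2 justifies the log scale by the skewness of A4, yet the baseline is averaged before the log is taken. Each post-baseline value is a single measurement; each baseline is an average of up to three. For a right-skewed variable the two are not centred at the same place on the log scale, so log change has a negative expectation under no change.

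What is at stake is the set of by-arm figures. Percent reductions per arm are planned outputs of the secondary analyses. The 13.4.1 plot would show every arm, placebo included, falling between baseline and the first post-baseline visit. Protocol 9.4.1 also calls for change-from-baseline summaries at every post-baseline time point. In Parts B and C all subjects take active drug, so hormone summaries after Week 18 have no concurrent placebo arm against which to see the offset.

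**Working it through.** The documents state no figure for baseline bias or for within-subject variability, so there is no plan figure to reproduce.

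**Illustration (invented values).** Baselines 400, 800 and 1600 ng/dL have arithmetic mean 933.3 and geometric mean 800. A post-baseline value of 800 is 800/933.3 - 1 = -14.3% against the first and 0% against the second.

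**Formula.** Let within-subject visit noise be log-normal, independent between visits, with log SD *s*, and let *k* be the number of baseline values. With no true change,

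E[log change] = -E[log(arithmetic mean of *k* values)] ≈ -(s²/2)(1 - 1/k), which is -s²/3 for k = 3.

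**Anchor in the documents.** The only variability figure is the 30% SD of percent change in Protocol 9.2 and SAP 7. Suppose that all of it is within-subject noise:
- SD of log change = √ln(1 + 0.30²) = 0.294.
- Change from a three-value baseline has variance s²(1 + 1/3), so s = 0.294/√(4/3) = 0.254 (CV about 26%).
- Approximate offset = -0.254²/3 = -0.0215, that is -2.1%.

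**Range (k = 3).** Log SDs of 0.3 to 0.6 are assumptions.

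| Within-subject log SD | E[log of arithmetic mean] | Spurious within-arm change | Approximation |
|---|---|---|---|
| 0.254 (from the 30% SD) | 0.021 | -2.1% | -2.1% |
| 0.3 | 0.030 | -2.9% | -3.0% |
| 0.4 | 0.052 | -5.1% | -5.2% |
| 0.5 | 0.080 | -7.7% | -8.0% |
| 0.6 | 0.114 | -10.7% | -11.3% |

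The second and third columns come from simulation (2,000,000 draws per setting) and agree with numerical integration. With the logs averaged, the null change is 0% throughout.

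**Number of baseline values.** At CV 50% (log SD 0.472) the offset is 0% for one value, about -5% for two and about -7% for three.

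**Effect on contrasts.** A four-arm ANCOVA was simulated with 18 per arm, log baseline as covariate, an assumed between-subject log SD of 0.7 and 4,000 trials. It is a single-time-point stand-in for the random-coefficients model. With CV 50% and a true drug/placebo ratio of 0.50:

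| Baseline | Placebo | Drug | Drug/placebo ratio |
|---|---|---|---|
| Arithmetic mean | -7.0% | -53.5% | 0.500 |
| Mean of logs | -0.1% | -50.0% | 0.500 |

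Under the null at CV 30%, 50% and 80%, type I error was 4.7%, 5.4% and 5.2% with the arithmetic baseline, and 4.8%, 5.2% and 5.1% with the mean of logs.

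**Primary test.** In SAP 13.3.3 "the model will be fitted with and without the randomized treatment by time and randomized treatment by time squared interactions terms". An offset that is constant over time and has the same expectation in all randomised arms falls into the intercept and baseline terms, not into those interactions.

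**Appendix E.** The code recovers baseline as mean log A4 minus mean log change. This returns the same averaged baseline, so a within-arm absolute change measured from it inherits the offset. The drug-minus-placebo absolute difference is formed from the two post-baseline means and does not.

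**Individual percent change.** SAP 9.3.12: "Percent change from baseline is calculated for the individual subject as the change from baseline divided by the baseline assessment". Its mean moves the other way under no change: +2.2% at CV 26% and +8.2% at CV 50%.

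**The case against.** The strongest reply is that nothing inferential is touched. SAP 13.4.1 names the drug-placebo ratio as the measure of treatment effect, and it is unbiased under either baseline. This stands, and it rules out several stronger readings that a reader might infer.

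- *Every reported percent change is overstated.* No. The placebo-adjusted percent effect is unaffected. The individual percent changes tabulated under SAP 13.3.4 have a mean that is biased upward.
- *The geometric-mean label in 13.4.1 is false.* No. The exponential of the mean log ratio is the across-subject geometric mean of post-baseline values divided by the across-subject geometric mean of the defined baselines, however each subject's baseline was formed. The problem is that a single value is set against a within-subject average.
- *The Week 76 results are contaminated because they are judged against baseline only.* Not the listed endpoints. Analyses 3.7 to 3.11 cover SF-36, acne, hirsutism, GC reduction and TART volume. A4 enters 3.10 only as a threshold against ULN. At most, descriptive hormone summaries at later visits are affected.

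Three further replies have force. *Arithmetic* is an inference from the bare word in 9.3.10. The larger offsets rest on assumed SDs. And a geometric baseline would not by itself stop placebo from appearing to improve: subjects qualify partly on elevated Week 4 A4, Week 4 is one of the three baseline values, and regression to the mean would remain.

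What survives is that a programmer following 9.3.10 as written would compute an arithmetic mean, and the planned by-arm log-scale figures would then be off in a known direction.

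**Conclusion.** The point holds for within-arm log-scale percent changes in A4, 17-OHP and ACTH, in every arm including placebo, and for the within-arm absolute changes derived from them. Under no true change the offset is about -2% on the most generous use of the documents' 30% SD, and -2.9% to -10.7% for assumed within-subject log SDs of 0.3 to 0.6. It is smaller for subjects with fewer than three baseline values.

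These sizes assume that the average is arithmetic and that visit-to-visit noise is log-normal and independent; positive correlation between visits would shrink them. The documents do not support reading this as a bias in the primary test, in any drug-placebo estimate or in a listed Week 76 endpoint. It is a correction to planned secondary outputs and does not threaten the trial's main conclusion.

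**What to change.** In SAP 9.3.10, define the A4, 17-OHP and ACTH baseline for all log-scale analyses, and for the log-baseline covariate, as the mean of the log values at Day 1, Week 4 and Week 6. This removes the offset and its dependence on how many baseline values a subject has.

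Keep the arithmetic mean for raw-scale descriptive change, where it is unbiased under no change. Label the two baselines in 9.3.10, in the 13.3.4 tables and in the Appendix E output, and say which one defines the baseline A4 subgroup in 10.7. Add a sentence that within-arm percent changes are descriptive and are to be read against placebo, because regression to the mean from selection on Week 4 A4 would remain.

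The cost is two labelled baselines per hormone and consistent edits in those sections. No new data are needed, and the expected drug-placebo contrast does not change.
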